## 12.4 Safety

### 12.4.1 Adverse events

AE onset day and AE duration are defined as follows:

AE onset day

- AE start date – date of first study drug intake in C203 + 1 day (when the AE start date is completely known)
- missing (when the AE start date is incomplete or unknown).

#### AE duration

- AE stop date – AE start date + 1 day (when both dates are completely known)
- trial termination date – AE start date + 1 day (when the AE start date is fully known but the AE is not resolved at the end of the trial): in this case the duration will be presented as “>x days” in the listing rather than “x days”
- missing (when the AE start date is incomplete or unknown, or when the AE has resolved but with an incomplete or unknown end date).

#### 12.4.2 Laboratory

Values will be scored as abnormally low (L), normal (N) or abnormally high (H). A value is classified as abnormally low when the value < lower limit of the normal range. A value is classified as abnormally high when the value > upper limit of the normal range. Tests without normal ranges will not be scored.

An original value like “<X” where X equals the lower limit of the normal range will be classified as abnormally low (L). An original value like “>X” where X equals the upper limit of the normal range will be classified as abnormally high (H).

Urinalysis tests for which a normal range is available, will also be categorized as L, N, or H. If there is doubt on whether the result is within normal range or not, the worst-case will be taken. E.g., when the test result equals “4 to 6” and the normal range is 0-5, then the test result will be classified as abnormally high (H) if it is a post-baseline visit, and will be classified as normal (N) if it is a baseline visit. In such cases, the original urinalysis test result will not be used for the tables, but will only be listed. Urinalysis tests for which no normal range is available, will be tabulated separately as categorical data.

All nonmissing post-baseline values (including unscheduled measurements and follow-up measurements) will be used to derive the following worst-case abnormalities for each parameter:

- H = abnormally high: at least one postdose measurement is above the normal range, and there are no values below the normal range.
- L = abnormally low: at least one postdose measurement is below the normal range, and there are no values above the normal range.
- H+L = abnormally high and low: at least one postdose measurement is above the normal range, and at least one other postdose measurement is below the normal range.
- N = normal: all postdose measurements are within normal limits.

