3.6.6. EVALUATION OF SAFETY PARAMETERS

The DSMB will evaluate the safety data periodically (see section [3.4.5](#)).

The following analyses will be performed to assess the safety of subjects in this study:

- The incidence and type of AEs.
- The incidence and type of SAEs.
- The incidence and type of related AEs (including study drug injection-site reactions and hypersensitivity reactions).
- The laboratory parameters and change from baseline in these laboratory parameters.
- The incidence of antibodies to ALX-0061.

All safety and immunogenicity analyses will be performed using the Safety Population of all subjects who received at least 1 dose of study drug. In addition, subgroup analyses will be performed to evaluate consistency of safety over

covariates including demographics (including weight) and concomitant medication (including immunosuppressants and corticosteroids).

AEs will be fully described and coded according to the Medical Dictionary for regulatory Activities. A treatment-emergent analysis of AEs will be done. Frequency of subjects presenting AEs, AEs leading to withdrawal, adverse drug reactions, and SAEs will be tabulated by system organ class and preferred term.

For laboratory parameters, descriptive statistics (mean, median, standard deviation, minimum, and maximum) will be computed on the actual values and the change from baseline (absolute) for each parameter. All laboratory values will be categorized according to their normal ranges as below, within or above normal. A shift table versus baseline (including final value versus baseline and worst value versus baseline) will be created.

Vital signs variables will be fully depicted using descriptive statistics (for actual values and changes from baseline).

Abnormal findings in physical examinations will be listed.

Immunogenicity will be assessed through listing of individual results by subject and summary tables.

Note that baseline refers to the baseline value of the preceding Phase IIb study with ALX-0061 (ALX0061-C201 or ALX0061-C202) the subject was enrolled in.

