**Safety endpoints:**

- Number of events as well as number and percentage of subjects with treatment-emergent Adverse Events (TEAEs), treatment-related AEs, Serious Adverse Events (SAEs), non-serious AEs, treatment-related SAEs, SAEs leading to treatment discontinuation and Adverse Events of Special Interest (AESI), categorized by System Organ Class (SOC) and Preferred Term (PT) and Maximum Severity (where applicable). Note that all adverse events reported in this study are considered treatment-emergent.
- Actual values and change from baseline in clinical laboratory parameters, including blood chemistry, hematology, urinalysis, coagulation and the acute phase proteins (CRP, ESR, and fibrinogen) at Week 0, Week 4, Week 8, Week 12, Week 24, Week 36, Week 48, Week 60, Week 72, Week 84, Week 96, Week 104 and Follow-up (Week 0, Week 24, Week 48, Week 72 and Week 104 only for extended clinical laboratory analyses).
- Shift from baseline in clinical laboratory parameters with normal ranges or CTCAE grades at Week 0, Week 4, Week 8, Week 12, Week 24, Week 36, Week 48, Week 60, Week 72, Week 84, Week 96, Week 104 and Follow-up.
- Actual values and change from baseline values in vital signs measurements at Week 0, Week 4, Week 8, Week 12, Week 24, Week 36, Week 48, Week 60, Week 72, Week 84, Week 96, Week 104 and Follow-up.
- Physical examination abnormal findings at Week 0, Week 12, Week 24, Week 36, Week 48, Week 60, Week 72, Week 84, Week 96, Week 104 and Follow-up.

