### 4.2 Key Definitions and Labels

#### 4.2.1 *Definition of baseline and change from baseline*

The baseline value will be the baseline value of the parent study.

The absolute change from baseline will be calculated for all post-baseline time points as:  
Change from baseline at time point t = value at time point t – baseline value

For selected efficacy endpoints, the percentage change from baseline will be calculated for all post-baseline time points as: Percentage change from baseline at time point t =  $100 * (value at time point t - baseline value) / baseline value$ . As percentage change can not be calculated for subjects with a baseline value of 0, these subjects will not be included for the corresponding summary analysis (if planned) and the respective column(s) will be kept blank for the corresponding listing.

For the changes from baseline, only subjects with both a baseline value and a value at the post-baseline time point will be included.

Wherever in the document 'change from baseline' is mentioned, it concerns the absolute change from baseline.

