## 7 SAFETY

### 7.1 Adverse Events

All safety summaries will be based on the safety population and presented by treatment group (see section 4.2.2). As study drug treatment is not interrupted between the parent study and this study, all adverse events reported in this study are considered treatment-emergent. However, unless specified otherwise, only adverse events that started after the first dose of C203 will be considered in the tables.

All adverse events will be coded and classified by System Organ Class (SOC) and Preferred Term (PT) using the medical dictionary for regulatory activity (MedDRA) that is current at the time of database lock.

A TEAE will be categorized as study drug-related if the relationship to study drug is reported to be 'possibly related' or 'related', or missing. In tabulations this categorization

will be used, but in the listings the original reported relationship will be presented. If the relationship is reported to be 'not applicable', it will not be considered in the tabulations.

A TEAE is reported as related to study procedure or not related to study procedure. Missing study procedure relationship will be considered as related.

A general summary table with AE events starting after first dose of C203 only will be produced to report the number and percentage of subjects with at least one event, the number of events and the incidence per 100 patient years, which will be calculated as:  $100 \times (\text{Number of subjects with AE}) / (\text{Total number of years observed while on C203, summed for all subjects})$ . Percentages will be calculated out of the number of subjects in the relevant treatment group.

The following categories will be included in the summary table:

- TEAE
- serious TEAE
- TEAE leading to death
- severe TEAE as classified by the investigator
- TEAE for which the study drug was interrupted
- TEAE for which the study drug was discontinued
- study drug-related TEAE
- serious study drug-related TEAE
- injection-site reaction.

Note that the TEAE here refers to the AEs starting after first dose of study drug in C203 study.

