**Table 14.3.2.5: Laboratory data: Cross-tabulation of the worst-case abnormalities**

Cross-tabulation per lab test category (hematology, biochemistry, acute phase proteins, urinalysis, coagulation) and lab test.

Population: safety population.

**Table 14.3.2.6: Laboratory data: Cross-tabulation of the worst-case CTCAE toxicity for key hematology and biochemistry parameters**

Cross-tabulation per lab category and lab test.

Population: safety population.

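### SAP 12.4.2 does not settle whether the worst-case laboratory category starts after the parent-study baseline or after the first C203 dose, so a pre-C203 Week 0 value can set it

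*SAP*

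**What the plan says.** SAP 4.2.1 fixes the reference: "The baseline value will be the baseline value of the parent study". Protocol 3.6.6 says the same for safety. SAP 12.4.2 then names the values that feed the worst-case category: "All nonmissing post-baseline values (including unscheduled measurements and follow-up measurements) will be used to derive the following worst-case abnormalities for each parameter". The categories listed directly below use another term. High, for example, requires "at least one postdose measurement is above the normal range, and there are no values below the normal range". Low, high-and-low and normal are worded in the same way, and none says which dose is meant.

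Week 0 is treated as a time point later than baseline. SAP 3.3 lists among the safety endpoints: "Shift from baseline in clinical laboratory parameters with normal ranges or CTCAE grades at Week 0, Week 4, Week 8, Week 12". Footnote B of the schedule of assessments (Protocol, and SAP Appendix 1) says that the Week 0 laboratory results are those drawn at parent Week 22 (C201) or Week 10 (C202).

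The results go into SAP Table 14.3.2.5, "Laboratory data: Cross-tabulation of the worst-case abnormalities". Its columns are the groups of SAP 4.2.2, all labelled ALX-0061 150 mg q2w (with MTX for C201), with the parent-study regimen in brackets. For adverse events, SAP 7.1 sets a boundary: unless otherwise specified, "only adverse events that started after the first dose of C203 will be considered in the tables".

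**The concern.** The worst-case table pools over time, so a reader cannot see which sample produced a category. If Week 0 counts, a subject whose C203 values are all normal can be shown as abnormal because of a sample drawn before the first C203 dose. In the former C201 placebo group that sample precedes all ALX-0061, yet the column carries the ALX-0061 label.

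The direction matters most for CRP, ESR and fibrinogen, which Protocol 1.2.5 describes as falling on ALX-0061. A high Week 0 value in that group reflects disease activity on placebo plus MTX, and would stand as the worst value on study drug. In the other groups Week 0 was on ALX-0061, but often on another regimen than the one in the label.

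The main adverse event tables have a boundary at the first C203 dose. The laboratory worst case has none, and SAP 11 (changes from the protocol analysis) does not mention the difference.

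**Working it through.** The plan gives no figure to reproduce. The check has two parts: what the text allows, and how much one extra value could change.

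**1. Which values qualify under each reading**

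- *Post-baseline, literal*: baseline is the parent baseline, and Week 0 is a listed shift time point. Week 0 is included in every group.
- *Postdose, after first study drug in the parent study*: Week 0 is included in every group. SAP 7.1 invites this reading, because it calls treatment uninterrupted between the studies.
- *Postdose, after first ALX-0061*: Week 0 is excluded for former placebo subjects and included for the rest. Columns of one table then follow different rules.
- *Postdose, after first C203 dose*: Week 0 is excluded everywhere. The SAP does not say this.

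The visit windows in SAP 12.1.1 do not decide the matter. They have no Week 0 row, but 12.4.2 takes all values, including unscheduled ones, and not only windowed visits.

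**2. Groups affected**

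SAP 4.2.2 lists 8 parent-regimen groups: 5 from C201 and 3 from C202. One is former placebo. Two had 150 mg q2w in the parent study. The other 8 − 1 − 2 = 5 had a different ALX-0061 regimen when the Week 0 sample was drawn.

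**3. The rule applied to single subjects**

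The C203 laboratory times after Week 0 are Weeks 4, 8, 12, 24, 36, 48, 60, 72, 84, 96, 104 and Follow-up, which is 12. Protocol Table 2 agrees (8 routine + 4 extended = 12).

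- Week 0 high, 12 later values normal: literal lead-in gives H; values after the first C203 dose give N.
- Week 0 high, one later value low, rest normal: H+L against L.
- Week 0 high, at least one later value also high and none low: H either way.

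So Week 0 matters only when no later value is abnormal in the same direction.

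**4. Size at constant prevalence, independent draws**

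Assume a probability p of abnormality at each draw and n draws after the first C203 dose. P(at least one abnormal) = 1 − (1 − p)^n. Adding Week 0 raises it by p(1 − p)^n.

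| p | n = 12 | with Week 0 | gain | n = 3 | with Week 0 | gain |
|---|---|---|---|---|---|---|
| 2% | 21.5% | 23.1% | 1.6 | 5.9% | 7.8% | 1.9 |
| 5% | 46.0% | 48.7% | 2.7 | 14.3% | 18.5% | 4.3 |
| 10% | 71.8% | 74.6% | 2.8 | 27.1% | 34.4% | 7.3 |

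Gains are in percentage points, from unrounded values.

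**5. Size with within-subject correlation**

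Latent-normal simulation, 200,000 subjects per scenario, correlation 0.3 and then 0.6:

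- 10% at every time, n = 12: 53.7% to 55.6%, and 38.4% to 39.4%.
- 10% at every time, n = 3: 24.0% to 29.3%, and 20.6% to 24.0%.
- Acute-phase marker in the former placebo group, 5% high per visit on drug, n = 12, 30% high at Week 0: 34.2% to 48.2%, and 23.6% to 37.5%.
- The same with 60% high at Week 0: 34.3% to 67.9%, and 23.4% to 61.6%.

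A repeat with another random seed agreed within about 0.3 points. All prevalences and correlations are assumptions.

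**The case against.** The best defence is that the definitions, not the lead-in, decide the category, and all four speak of postdose measurements. A value taken on placebo is not postdose to ALX-0061, so the group of most concern may already be protected. It is true that nothing in the SAP ranks the lead-in above the definitions, so calling the rule plainly wrong would go too far. But the defence needs an anchor dose that the SAP does not supply, and under the after-first-ALX-0061 reading Week 0 stays in for the other seven groups.

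Several limits on the harm also stand.

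- Protocol exclusion 12 is applied to the same sample. ALT or AST at 2 × ULN or more, neutrophils below 1.5 × 10⁹/L and platelets at or below 75 × 10⁹/L are excluded, so an eligible subject's Week 0 value is at most CTCAE grade 1 for these. Criterion 12f also removes other results judged clinically significant. Out-of-range values not so judged can still enter, for example ALT between 1 and 2 × ULN, or a raised CRP.
- The table is a cross-tabulation against parent baseline. A subject already high there is shown as high to high, which hides a normalisation but does not create a new abnormality.
- The on-drug course is visible by visit in Tables 14.3.2.1 and 14.3.2.3, and for CRP and ESR in Table 14.2.1.11.1.
- Former placebo subjects were on MTX and had at least 20% improvement in swollen and/or tender joint count. Their Week 0 values are not untreated disease.
- The adverse event comparison is not absolute: Tables 14.3.1.2 and 14.3.1.4 deliberately add parent-trial events. But they say so in their titles, which the laboratory table does not.

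**Conclusion.** SAP 12.4.2 is internally inconsistent about which values enter the worst case. On its lead-in, a Week 0 value drawn before any C203 dose can set the category in Table 14.3.2.5. This can misattribute a result in a safety table, so it is more than a missing detail, but it is limited to one sample per subject and to subjects with no later abnormality in the same direction.

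At constant prevalence the inflation is about 1 to 3 points for completers, and about 2 to 7 points for subjects with only three samples after the first C203 dose. For acute-phase markers in the former placebo group it could be much larger: 23–34% high becomes 38–68% if 30–60% were high at Week 0 and 5% per visit on drug. The documents give none of these prevalences, so these figures are illustrations and not predictions.

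A reader might infer two stronger points that the documents do not support. First, that every parent-study laboratory visit after baseline enters the table: only the Week 0 value is clearly carried into C203 laboratory analyses. Second, that the worst-case CTCAE table is shown to have the same fault: 12.4.2 defines only H, L, H+L and N, and Table 14.3.2.6 has no stated value set. There the established gap is a missing rule, and inclusion of Week 0 is an inference.

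**What to change.** In SAP 12.4.2, define the worst case from values collected after the first C203 study drug dose, including unscheduled and follow-up values. Use that one term in the lead-in and in all four category definitions. State that it applies to both the normal-range categories (Table 14.3.2.5) and the CTCAE grades (Table 14.3.2.6), which also closes the gap for the second table. Keep the parent-study baseline as the shift reference and Week 0 as a displayed by-visit time point.

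The cost is one phrase and one date filter, with no new data. The downside is slightly fewer flagged abnormalities. The Week 0 values stay visible in the by-visit tables.

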### 13 INDEX OF TABLES

#### 13.1 General

##### **Table 14.1.1.1: Subject disposition: Tabulation by analysis population**

Tabulation of the number of subjects in each of the analysis populations defined in section 4.1.

Population: all screened population.

**Table 14.1.1.2: Subject disposition: Tabulation by region and country**

Tabulation of the number of subjects per region and country.

Population: ITO population.

**Table 14.1.1.3: Subject disposition: Tabulation by time point**

Tabulation of the number of subjects per time point.

Population: ITO population.

**Table 14.1.1.4: Trial termination: Tabulation**

Tabulation of study completion / study discontinuations and the primary reason for discontinuation.

Population: ITO population.

**Table 14.1.1.5: Major protocol deviations: Tabulation**

Tabulation of the major protocol deviations per category including Selection criteria not met / Subject not withdrawn as per protocol / Prohibited concomitant medication / Treatment non-compliance / Safety assessment deviation / Efficacy assessment deviation / Other.

Population: ITO population.

**Table 14.1.2.1: Demographic data: Tabulation and descriptive statistics**

Descriptive statistics for continuous parameters and frequency tabulation for categorical parameters.

Population: ITO population.

**Table 14.1.2.2: Baseline disease characteristics: Tabulation and descriptive statistics**

Descriptive statistics for continuous parameters and frequency tabulation for categorical parameters.

Population: ITO population.

**Table 14.1.2.3: Tabulation of RA related concomitant therapies by generic term**

Tabulation of the generic terms of RA related concomitant therapies.

Population: safety population.

**Table 14.1.2.4: Tabulation of non-RA related concomitant therapies by generic term**

Tabulation of the generic terms of non-RA related concomitant therapies.

Population: safety population.

**Table 14.1.2.5: Exposure to study medication: Descriptive statistics**

Descriptive statistics of exposure parameters except home administration, including compliance.

Population: safety population.

**Table 14.1.2.6: Exposure to study medication: Home administration**

Tabulation of any study drug administration received at home (yes/no) and of all study drug administrations received at home, except those received during a scheduled study visit (yes/no).

Population: safety population.

## 13.2 Efficacy

### **Table 14.2.1.1.1: ACR response - ACR20 response**

Frequency tabulation of the ACR20 response at each time point, including a Wilson score 95% CI on the percentage of subjects achieving ACR20 response.

Population: ITO.

### **Table 14.2.1.1.2: ACR response - ACR50 response**

Frequency tabulation of the ACR50 response at each time point, including a Wilson score 95% CI on the percentage of subjects achieving ACR50 response.

Population: ITO.

### **Table 14.2.1.1.3: ACR response - ACR70 response**

Frequency tabulation of the ACR70 response at each time point, including a Wilson score 95% CI on the percentage of subjects achieving ACR70 response.

Population: ITO.

### **Table 14.2.1.1.4: ACR response - ACR-N index of improvement**

Descriptive statistics of the ACR-N index actual values at each time point.

Population: ITO.

### **Table 14.2.1.2.1: DAS28 Score – Actual values and change from baseline**

Descriptive statistics of the DAS28(CRP) and the DAS28(ESR) score actual values and change from baseline at each time point. Additionally, the change from baseline at each time point will be modelled using an ANCOVA model with treatment group and baseline DAS28 score as covariates and the LS means with 95% CI will be reported.

Population: ITO.

### **Table 14.2.1.2.2: DAS28 Score – EULAR (using CRP and using ESR) response**

Frequency tabulation of the EULAR response, based on the DAS28(CRP) and the DAS28(ESR) score at each time point, including a Wilson score 95% CI on the percentage of subjects achieving EULAR response.

Population: ITO.

### **Table 14.2.1.2.3: DAS28 Score – Disease activity (ESR)**

Frequency tabulation of the disease activity, based on the DAS28(ESR) score at each time point, including a Wilson score 95% CI on the percentage of subjects achieving LDA/remission, remission and maintained remission.

Population: ITO.

### **Table 14.2.1.2.4: DAS28 Score – Disease activity (CRP)**

Frequency tabulation of the disease activity, based on the DAS28(CRP) score at each time point, including a Wilson score 95% CI on the percentage of subjects achieving DAS28(CRP)  $\leq 3.2$ , DAS28(CRP)  $< 2.6$  and maintained DAS28(CRP)  $< 2.6$ .

Population: ITO.

**Table 14.2.1.3.1: Boolean disease remission definition**

Frequency tabulation of the disease remission, based on the Boolean definition at each time point, including a Wilson score 95% CI on the percentage of subjects achieving remission and maintained remission.

Population: ITO.

